**IV. SUBJECT ENROLLMENT**

We propose to recruit 150 patients for CIRT-CFR. This will be a collaborative effort between 6 clinical sites, with 4 sites in the Boston area: (1) *Brigham and Women's Hospital, BWH* (PI: [name]), (2) *Joslin Diabetes Center* (PI: [name]), (3) *Massachusetts General Hospital* (PIs: [name], and [name]), (4) *North Shore Medical Center* (PI: [name]), and two additional sites in the Ottawa area: (5) *Ottawa Heart Institute, OHI* (PI: [name]), and in Birmingham, Alabama: (6) *University of Alabama, UAB* (PI: [name]). We will have 3 imaging sites (BWH, PI: [name] [name]; OHI, PI: [name]; and UAB, PI: [name]), with **BWH serving as the Core Imaging Lab**, and all 4 Boston area sites referring patients for imaging to BWH. The subjects of the trial will be patients with CAD and type 2 DM or metabolic syndrome enrolled in the parent study (CIRT) and recruited from participating

CIRT sites local to BWH, OHI, and UAB. All patients identified at the 6 participating clinical sites as being potentially eligible for CIRT are automatically eligible for participation in this ancillary study.

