## V. STUDY PROCEDURES

Randomization and double-blind study treatment period to either placebo or LDM (1:1) of willing and eligible patients will occur at the end of the open label run-in phase per the parent CIRT protocol, and will be stratified by time since the qualifying event ( $< 6$  or  $\geq 6$  months from the date of MI or most recent angiogram), type of event (MI or multivessel CAD), presence of either type 2 DM or metabolic syndrome, and site, which will ensure balance in the proposed study. Patients willing to participate in CIRT will be asked to enroll into the sub-study and may sign the CIRT-CFR informed consent at any point between signing the parent CIRT informed consent and completing the parent CIRT randomization visit (Visit 4). After giving informed consent for the ancillary CIRT-CFR, patients will undergo the baseline PET scan along with echocardiography at any point between the parent CIRT post run-in visit (Visit 3) and up to 4 weeks after randomization (Visit 4). Per the parent CIRT protocol: i) blood will be collected and stored for biomarkers at baseline (Visit 3), ii) patients will complete quality of life (SF-36) questionnaires at enrollment (Visit 2) and 1-12 months (Visit 7) after randomization, and iii) patients will be called at 3, 6, and 10 months after randomization to assure compliance. Final PET scan and echocardiogram will occur at approximately 1-12 months after randomization or within 4 weeks ( $\pm 2$  weeks) of Visit 7. At that time, blood will be collected and stored for biomarkers (using the same protocol as in the parent CIRT) to coincide with follow-up imaging in CIRT-CFR. The data collection schedule for CIRT and CIRT-CFR is summarized in the Appendix. Trial schema is as follows:

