## VI. BIOSTATISTICAL ANALYSIS

CIRT-CFR sites participating in the proposed ancillary study. Based on our power analysis and sample size calculations, we estimate that each of the 6 clinical sites will be required to enroll approximately 25 patients over approximately 3 years. This is equivalent to 1 patient every 6 weeks per site, which we believe is reasonable and attainable. All sites have received IRB approval for the parent study and are actively enrolling patients in the parent CIRT trial. The proposed imaging studies (PET scans and echos) are routinely performed at the 3 imaging sites (BWH, OHI, and UAB). Drs. [name] (PI) and [name] (both at BWH), [name] (OHI), and [name] (UAB) are recognized experts in quantitative PET imaging and echocardiography, have published widely on these topics, and have extensive experience in conducting clinical trials using imaging endpoints.

***Aim 1. To test the hypothesis that systemic inflammation is a critical determinant of coronary flow reserve (CFR) and myocardial tissue perfusion, as assessed by quantitative PET imaging, in stable CAD patients with type 2 DM or metabolic syndrome.*** Specifically, we propose that treatment with LDM at a target dose of 15 to 20 mg orally weekly for 1-12 months will, compared to placebo, result in:

***Hypothesis #1:*** Improved global CFR in response to dipyridamole, reflecting primarily endothelium-independent vasodilation.

***Hypothesis #2:*** Reduced total stress perfusion deficit, a semi-quantitative score combining scar and ischemia.

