**Methods:** PET scans will be performed at the 3 imaging sites at randomization and at 1-12-month follow-up using a standardized study protocol. As described in section V, we have previously demonstrated feasibility of measuring myocardial blood flow with high reproducibility. In addition to CFR and coronary hemodynamics, we will also measure the total perfusion deficit (TPD) during stress and at rest, and calculate the difference TPD between stress and rest (reflecting total ischemic burden) using previously validated methods. The primary endpoint for the efficacy portion of *Aim 1* is the change in global CFR response to dipyridamole, reflecting primarily endothelium-independent coronary vasodilatation, over 1-12 months. A key secondary endpoint is the change in dipyridamole-stimulated TPDstress, reflecting the combined extent and severity of ischemia and scar, over 1-12 months. Tertiary endpoints include the change in hyperemic global and regional (i.e., non-infarcted myocardium)

myocardial blood flow (MBF), and the change in global and regional TPDstress-rest (reflecting the ischemia score) over 1-12 months.

**Statistical analyses:** For the analyses of both primary and secondary endpoints included in *Hypotheses 1 and 2*, we will use separate linear regression models with the respective change in global CFR (in response to dipyridamole) and TPDstress over 1-12 months as the outcome variables. Each of these regression models will control for baseline variables of stratum (DM or metabolic syndrome), time since index MI (< 6 months or ≥6 months), imaging site (BWH or OHI), the corresponding baseline global CFR score, as well as treatment assignment. Although we expect the distribution of change scores to be approximately normal, preliminary analyses will evaluate whether a transformation from the Box-Cox family will improve that assumption. From our experience in prior clinical trials using a similar design to CIRT-CFR, we expect a 10-15% attrition rate of patients due to death or loss to follow-up. Because it is not expected that site randomization assignment will influence these events, and because the available information is unlikely to allow for accurate imputation of missing values for CFR, subjects who do not have a repeat 1-12-month PET scan will not be included in the primary or secondary analyses.

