**Power calculations:** For *Aim 1*, we used prior publications from our group to characterize the reproducibility of the global, dipyridamole mediated CFR measurements in patients with DM or metabolic syndrome. We used data from the patients enrolled in the placebo arm of these trials to estimate the standard deviation in the change in global CFR (Time 2 CFR – Time 1 CFR), and found a mean standard deviation of 0.45. **Table 1** shows the sample size needed to reach 80-90% power for an expected effect size of 20% relative improvement in CFR in the active treatment group compared to placebo. Using a total sample size of 130 evaluable patients and a two-tailed alpha of 0.05, power will be 85% for this analysis. Estimated power by this approach should be considered conservative since the control for baseline CFR is expected to enhance power. ***We expect to randomize approximately 150 patients*** to have at least 130 evaluable subjects completing the study (estimating a 10-15% attrition rate between time of randomization and final PET).

**Table 1.** Power and sample size calculations for Aim 1

AIM 1 Measurement	Difference (LDM vs. placebo)	Standard deviation (placebo)	Two-sided α level	Total sample size for power		
				80%	85%	90%
Primary outcome:						
ΔCFR to dipyridamole	0.24	0.45	0.05	114	130	150
Secondary outcome:						
ΔTPD stress	2.5%	4.9%	0.05	124	140	164

***Aim 2. To test the hypothesis that LDM at a target dose of 15 to 20 mg orally weekly for 1-12 months will, compared to placebo, result in improved LV myocardial mechanics, as assessed by transthoracic echocardiography, and that this functional improvement will correlate with the change in CFR after 1-12 months of treatment.*** Specifically:

***Hypothesis #3:*** LDM for 1-12 months will result in improved LV systolic function, as assessed by measures of LV peak global longitudinal strain, and diastolic function, as assessed by measures of tissue Doppler mitral annular early diastolic relaxation velocity (E’).

**Hypothesis #4:** Changes in LV systolic and diastolic function after 1-12 months of LDM therapy will be correlated with changes in coronary flow reserve.

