**Power calculations:** For *Aim 2*, we used prior publications from our team to characterize the reproducibility of the LV measures of systolic and diastolic function. Power analysis is based upon the following assumptions: the expected effect size is 10% relative improvement in each of the primary and secondary outcome measures in the active treatment group compared to placebo. **Table 2** shows the sample size needed to reach 80-90% power for each of the primary and secondary efficacy measures. As for *Aim 1*, estimated power by this approach should be considered conservative since the control for baseline scores is expected to enhance power. Of the 150 patients we expect to randomize, there will be at least 130 evaluable subjects completing the study (estimating a 10-15% attrition rate between time of randomization and final echo).

**Table 2.** Power and sample size calculations for Aim 2

AIM 2 Measurement	Difference (LDM vs. placebo)	Standard deviation (placebo)	Two-sided $\alpha$ level	Total sample size for power		
				80%	85%	90%
Primary outcome:						
Systolic: $\Delta\text{GLS}_{\text{peak}}$	1.4%	2.8	0.05	126	142	166
Diastolic: $\Delta\text{E}'_{\text{velocity}}$	0.7 cm/s	1.3	0.05	112	126	148
Secondary outcomes:						
Systolic: $\Delta\text{S}'$	0.6 cm/s	1.2	0.05	128	146	172
$\Delta\text{LVEF}$	1.5%	3.1	0.05	138	156	182
Diastolic: $\Delta\text{E}/\text{E}'$	1.1	2.0	0.05	128	146	172
$\Delta\text{LAVI}$	1.2 ml/m 	2.3	0.05	118	134	158

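### At the plan's own 15% attrition, 150 randomized patients leave 127 evaluable, not at least 130; the effect on power is under one percentage point

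*Combined protocol and SAP*

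**What the plan says.** All references are to the combined protocol and SAP.

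- **Section VI, Aim 1, Power calculations.** About 150 patients are to be randomized "to have at least 130 evaluable subjects completing the study (estimating a 10-15% attrition rate between time of randomization and final PET"). The same paragraph states: "Using a total sample size of 130 evaluable patients and a two-tailed alpha of 0.05, power will be 85% for this analysis". The Table 1 row for the primary outcome reads "ΔCFR to dipyridamole 0.24 0.45 0.05 114 130 150": difference, SD, two-sided alpha, then total sample size for 80%, 85% and 90% power.
- **Section VI, Aim 2, Power calculations.** Of the 150 expected to be randomized, "there will be at least 130 evaluable subjects completing the study", with the same 10-15% allowance running from randomization to the final echocardiogram.
- **Section VI, Aim 1, Statistical analyses.** Here the allowance is described by cause: "we expect a 10-15% attrition rate of patients due to death or loss to follow-up". Patients without a repeat PET scan are left out of the primary and secondary analyses, and nothing is imputed.
- **Section IV.** "We propose to recruit 150 patients for CIRT-CFR".
- **Section VI, opening paragraph.** Each of the 6 clinical sites "will be required to enroll approximately 25 patients over approximately 3 years", which the text presents as a result of the power analysis.
- **Section V.** Randomization takes place at the end of the open-label run-in. Patients "may sign the CIRT-CFR informed consent at any point between signing the parent CIRT informed consent and completing the parent CIRT randomization visit".

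**The concern.** The plan gives a floor for the evaluable number and a range for attrition. A floor has to hold at the worst rate in the range, and this one does not. Because patients without a second PET scan drop out of the analysis, the evaluable number is the number on which power depends, and the plan ties its 85% to 130.

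A second, smaller matter is the unit in which the 150 is counted. It appears as patients recruited (section IV), enrolled (section VI, opening) and randomized (both power paragraphs). A patient may sign the sub-study consent before the run-in ends, and section I says the run-in serves to exclude, before randomization, those who cannot tolerate the drug. Recruited, enrolled and randomized are therefore not automatically the same count.

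**Working it through.** **Inputs.** Difference in change in CFR 0.24, SD 0.45, two-sided alpha 0.05 (Table 1); 1:1 allocation (section V); about 150 randomized, attrition 10-15%, floor of 130 (section VI, both power paragraphs).

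**Step 1: reproduce Table 1.** Two-sample t-test with equal arms and total N: degrees of freedom N - 2, noncentrality = difference / (SD x sqrt(4/N)). The smallest even N reaching 80%, 85% and 90% power is 114, 130 and 150, which matches the CFR row exactly. The normal approximation gives 112, 128 and 148, so the noncentral t is the method behind this row.

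**Step 2: apply the stated attrition.** Evaluable = 150 x (1 - attrition).

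| Attrition | Evaluable | Floor of 130 met? |
|---|---|---|
| 10% | 150 x 0.90 = 135 | yes |
| 12.5% | 150 x 0.875 = 131.25, so 131 | yes |
| 13.3% | 150 - 20 = 130 | just |
| 15% | 150 x 0.85 = 127.5, so 127 | no, 3 short |

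The floor fails for attrition between 13.3% and 15%, which is the top third of the stated range ((15 - 13.33)/5 = 0.33). For 130 evaluable at 15% attrition, 130/0.85 = 152.9, so 153 would have to be randomized. The figure of 150 is what 130 x 1.15 = 149.5 rounds up to, so it may come from multiplying by 1.15 instead of dividing by 0.85; the plan does not show its step.

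**Step 3: power at those numbers (CFR, noncentral t).**

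| Evaluable | Noncentrality | Power |
|---|---|---|
| 135 | 0.24 / (0.45 x sqrt(4/135)) = 3.10 | 86.8% |
| 130 | 0.24 / (0.45 x sqrt(4/130)) = 3.04 | 85.5% |
| 127 | 0.24 / (0.45 x sqrt(4/127)) = 3.01 | 84.7% |

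The loss from 130 to 127 is 0.8 of a point. By the normal approximation, power at 127 is 85.2%.

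**Step 4: the other endpoint close to a threshold.** For GLS (difference 1.4, SD 2.8, Table 2), noncentral t power is 80.8% at 130 and 79.8% at 127. The normal approximation gives 80.4% at 127. Table 2 lists 126 for 80% power on GLS, which agrees with the normal approximation and not with the noncentral t (128).

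**Step 5: the unit of the 150.** 6 sites x 25 = 150, the number that both power paragraphs place at randomization. The site target and the randomized target are therefore the same number, described with different words.

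**The case against.** **That the shortfall is trivial.** The plan says approximately 150, the midpoint of the attrition range leaves 131, and power at 127 still rounds to 85%. Both power paragraphs add that power is conservative because adjustment for the baseline value is ignored. All of this stands as to consequence. It does not rescue the sentence: a stated minimum that fails within its own stated range should be restated.

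**Stronger readings that a reader might infer.**

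- *Run-in failures come out of the 150 and leave the trial short of power.* If the 150 were counted at consent and 5-20% then failed the run-in (an assumed range; the documents give no rate), the evaluable number after 10-15% attrition would run from 150 x 0.95 x 0.90 = 128 down to 150 x 0.80 x 0.85 = 102, with CFR power from about 85% down to 76%. The documents do not support that premise. Both power paragraphs place the 150, and the start of attrition, at randomization. The 25 per site is derived from that calculation. Consent may also be signed after the run-in, up to completion of the randomization visit. Nothing closes recruitment at 150 consents. What stands is the loose terminology.
- *The allowance covers only death and loss to follow-up, so refused scans come on top.* The Aim 1 statistical analyses paragraph names those causes, but the power paragraphs define the allowance by its time window, without limiting it by cause. A declined second scan, or withdrawal after randomization but before the baseline scan, falls inside that window.
- *GLS falls below 80% power.* That depends on the method (79.8% or 80.4% at 127), and the plan's own Table 2 asks for only 126.

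**Conclusion.** The evaluable figure is wrong as written in both power paragraphs. At 10-15% attrition, 150 randomized patients give about 127-135 evaluable, and the floor of 130 holds only up to 13.3%. The cost to CFR power at the unfavourable end is under one percentage point (85.5% to 84.7%), so this is an error in a stated figure and not evidence of an underpowered trial. The result rests on the plan's own difference, SD, alpha and attrition range, on exactly 150 randomized in equal arms, and on an unadjusted two-sample comparison.

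The mixed wording for the 150 is an inconsistency to tidy. It does not establish a material loss of power, and the size of any run-in loss cannot be calculated from the documents.

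**What to change.** 1. In both power paragraphs of section VI, replace the floor of 130 with about 127-135 evaluable at 10-15% attrition. In the Aim 1 paragraph, give CFR power as about 84.7-86.8% (noncentral t, Table 1 inputs).
2. In section IV and in the opening paragraph of section VI, state that the 150 (25 per site) is counted at randomization, as the power paragraphs already do.

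**Cost.** Wording and restated figures only. The single downside is a slightly less favourable evaluable number. No patients are added to the 150 randomized already planned. Keeping the floor of 130 at 15% attrition would instead need 153 randomized, which a difference of under one point of power does not require.

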**Hypothesis #2:** Reduced total stress perfusion deficit, a semi-quantitative score that combines scar and ischemia.

**AIM 2.** To test the hypothesis that LDM at a target dose of 15 to 20 mg orally weekly for 1-12 months will, compared to placebo, result in improved left ventricular (LV) myocardial mechanics, as assessed by transthoracic echocardiography, and that this functional improvement will be correlated with the change in coronary flow reserve after 1-12 months of treatment. In this population of patients without severe heart failure, we propose to test the following hypotheses:

**Hypothesis #3:** LDM for 1-12 months will result in improved LV systolic function, as assessed by measures of LV peak global longitudinal strain, and diastolic function, as assessed by measures of tissue Doppler mitral annular early diastolic relaxation velocity (E').

**Hypothesis #4:** Changes in LV systolic and diastolic function after 1-12 months of LDM therapy will be correlated with changes in coronary flow reserve.

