**Methods:** 2-D echocardiograms will be performed at the 3 enrolling imaging sites at baseline and 12 months after randomization in accordance with standard clinical practice and utilizing a standardized study protocol as outlined in section V. As described in section V, we have previously demonstrated feasibility of measuring cardiac mechanics with high reproducibility. The primary efficacy endpoints for *Aim 2* are the change in LV peak global longitudinal strain (GLS) (systolic function) and in tissue Doppler mitral annular early diastolic relaxation velocity (E') (diastolic function). Key secondary endpoints are change in other LV systolic function measures (LVEF and tissue Doppler peak systolic mitral annular velocity (S')), as well as change in other LV diastolic function measures (LV early diastolic strain rate by speckle-tracking, and mitral inflow Doppler E velocity to E' ratio (E/E')). Tertiary endpoints include changes in more conventional measures of LV structure (e.g. volumes, wall thickness, mass) over 1-12 months.

**Statistical analyses. Hypothesis 3:** We will use separate linear regression models with the respective change in LV peak GLS and E' over 1-12 months as the outcome variables. Each of these regression models will control for baseline variables of stratum (DM or metabolic syndrome), time since index MI (< 6 months or ≥ 6 months), imaging site (BWH, OHI, or UAB), the corresponding baseline LV peak GLS and E' scores, as well as treatment assignment.

**Hypothesis 4:** Although temporality cannot be established in correlational analysis of concurrent changes, we will also use regression models to clarify the association of changes in CFR and LV function. Controlling for treatment assignment, baseline stratification variables, baseline CFR and LV function, as well as change in LV function, our outcome will be change in CFR. By adding the baseline and change in LV function to our primary model for *Aim 2*, we will explore whether changes in CFR are associated with changes in LV function, or whether independent treatment effects remain.

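### Hypothesis 4 is worded for patients on LDM, but its model estimates one LV-change slope over both arms, so the planned result cannot show whether the link holds under LDM

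*Combined protocol and SAP*

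**What the plan says.** Hypothesis 4 appears in Section II and again in Section VI: "Changes in LV systolic and diastolic function after 1-12 months of LDM therapy will be correlated with changes in coronary flow reserve". Aim 2 ties the correlation to the benefit of LDM over placebo. In Section II it says that "this functional improvement will be correlated with the change in coronary flow reserve after 1-12 months of treatment", and Section VI repeats this almost word for word.

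The analysis is set out in Section VI, Aim 2, Statistical analyses, Hypothesis 4. The model is specified as "Controlling for treatment assignment, baseline stratification variables, baseline CFR and LV function, as well as change in LV function, our outcome will be change in", where the sentence goes on to name CFR. The stated purpose is that "we will explore whether changes in CFR are associated with changes in LV function, or whether independent treatment effects remain". The only caveat is that "temporality cannot be established in correlational analysis of concurrent changes".

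Neither this paragraph nor the exploratory analyses at the end of Section VI give a treatment-by-LV-change term, a fit in LDM patients alone, or a slope by arm.

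**The concern.** The hypothesis is about patients on LDM, while the model describes everyone. Because treatment is a covariate, the mean shift that LDM may produce in LV function and CFR is removed from the LV-change coefficient. What remains is how the two changes move together within arms, and about half of that information comes from placebo patients. The model assumes equal slopes without saying so.

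Two readings of the result are then open to error. A significant pooled slope could be reported as a link under LDM when the LDM patients contribute little to it. A non-significant one could be reported as no link when a link exists under LDM but has been diluted. The plan's caveat concerns temporality and does not cover either case.

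**Working it through.** **Inputs from the documents.** Allocation is 1:1 (Section V). At least 130 evaluable patients are expected (Section VI, both power paragraphs), so 65 per arm. Two-sided alpha is 0.05. The CFR difference is 0.24 with SD 0.45 (Table 1), and the GLS difference is 1.4 with SD 2.8 (Table 2).

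**Assumed.** The within-arm correlation r between LV change and CFR change is not given anywhere, so a range is used. LV-change variance is taken as equal in the arms.

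**The plan's own figure.** No power is stated for Hypothesis 4. The Aim 1 figure reproduces: 0.24 / (0.45 × √(2/65)) = 0.24 / 0.0789 = 3.04, and Φ(3.04 − 1.96) = 86%, against 85% stated. A noncentral-t calculation returns the 114 / 130 / 150 of Table 1 exactly.

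**What the pooled slope estimates.** With equal arm sizes and equal LV-change variance, pooled slope = (LDM slope + placebo slope) / 2. Take r = 0.4 under LDM and 0 under placebo. The LDM slope is 0.4 × 0.45 = 0.180 CFR units per SD of LV change, and the pooled slope is (0.180 + 0) / 2 = 0.090. With the arms reversed it is again 0.090. The pooled slope cannot tell the two cases apart.

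**Approximate power, in SD units.** The planned model has nine coefficients (intercept, treatment, DM or metabolic syndrome, time stratum, two site terms, baseline CFR, baseline LV, LV change). Residual degrees of freedom are 130 − 9 = 121, or about 60.5 per arm, and the critical t is 1.98.

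*Link of 0.35 under LDM only:*
- Pooled: slope 0.35 / 2 = 0.175; SE = √((1 − 0.175²) / 121) = 0.0895; ratio 1.96; Φ(1.955 − 1.98) = 49%.
- LDM arm: residual variance ((1 − 0.35²) + 1) / 2 = 0.939; SE = √(0.939 / 60.5) = 0.125; ratio 2.81; Φ(0.83) = 80%.
- Slope difference: SE = √(2 × 0.939 / 60.5) = 0.176; ratio 1.99; Φ(0.01) = 50%.

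*Link of 0.25 in both arms:*
- Pooled: SE = √((1 − 0.25²) / 121) = 0.088; ratio 2.84; Φ(0.86) = 80%.
- LDM arm: SE = √(0.9375 / 60.5) = 0.1245; ratio 2.01; Φ(0.03) = 51%.

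**Simulation.** The planned model was compared with the same model plus a treatment-by-LV-change term, at 65 per arm and 6,000 replicates per scenario. Mean LDM effects were 0.24/0.45 = 0.533 SD on CFR and 1.4/2.8 = 0.5 SD on LV function, set to zero in the rows where both arms share a correlation of 0.10 to 0.25.

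| r under LDM | r under placebo | Pooled slope significant | LDM-arm slope significant |
|---|---|---|---|
| 0 | 0 | 5% | 5% |
| 0.35 | 0 | 50% | 80% |
| 0.40 | 0 | 60% | 89% |
| 0 | 0.25 | 28% | 6% |
| 0 | 0.35 | 50% | 6% |
| 0 | 0.50 | 80% | 7% |
| 0.10 | 0.10 | 19% | 12% |
| 0.20 | 0.20 | 61% | 35% |
| 0.25 | 0.25 | 80% | 51% |

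Independent runs of 4,000 replicates agree within simulation error. They also put the power of the slope-difference test at about 50% for 0.35 against 0.

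**The case against.** A reader might infer that placebo patients alone can confirm Hypothesis 4, and so that the plan contains an invalid test. The documents do not support that. The model is there to explore an association; Hypothesis 4 has no alpha, power, effect size or decision rule; and the primary endpoint and Hypotheses 1 to 3 do not depend on it. Against this, it is one of four numbered hypotheses under an aim framed as a test, and it is not listed among the exploratory objectives. The LV-change coefficient is the only quantity in the model that speaks to it.

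A reader might also take the last three rows of the table as false positives produced by ordinary visit-to-visit co-movement. They are not: in those rows the correlation under LDM is not zero, so the hypothesis as worded is true. The LDM-arm slope picks up such co-movement too. Only the slope difference separates it.

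A third inference is that the trial's mechanism requires a link existing only under LDM. Section I states a general principle, that better perfusion may improve cardiac mechanics. That fits a common slope along which LDM moves patients. Equal slopes would therefore not count against the mechanism, and a pooled, treatment-adjusted slope is a reasonable way to study it.

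Two further points stand. If the slopes are equal, replacing the pooled test by the LDM-arm slope would lose 80 − 51 = 29 points at r = 0.25, about the same as the 80 − 50 = 30 points gained when a link of 0.35 exists only under LDM. So the pooled slope should not be replaced. And placebo patients are not LDM-naive: Sections I and V put open-label LDM before randomization and baseline imaging after that run-in, so placebo-arm change runs from recent LDM exposure to a period without it.

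What survives is that the hypothesis names LDM-treated patients, the model does not isolate them, and the plan does not say so.

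**Conclusion.** The mismatch between hypothesis and model is in the text. The planned slope answers whether concurrent changes are associated across both arms. It cannot answer whether they are associated among patients on LDM. A one-arm link is roughly halved: for a correlation of 0.35, about 50% power pooled against 80% for the LDM-arm slope if the link is under LDM, and a significant pooled slope about 50% of the time if the link is under placebo only.

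These sizes rest on assumed correlations, 65 evaluable patients per arm and similar LV-change variance; if the variances differ, the arm with the larger one gets more weight. Nothing in the documents suggests that a placebo-only link is likely, so those rows illustrate the ambiguity and do not predict an error rate. This is a worthwhile, low-cost improvement to an exploratory analysis.

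**What to change.** In Section VI, Aim 2, Statistical analyses, Hypothesis 4:

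1. Keep the pooled slope as planned, and describe it as the association of concurrent changes in both arms combined.
2. Add a treatment-by-change-in-LV-function term. Report the LDM-arm slope, the placebo-arm slope and their difference, each with a 95% confidence interval.
3. Describe a link under LDM only as far as the LDM-arm slope supports it, and an LDM-specific link only if the slope difference supports it.
4. State that placebo-arm changes follow open-label LDM in the run-in, so the placebo slope reflects change after LDM is stopped.

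The cost is one model term and a few sentences, with no new data. The downside is imprecision: the slope difference has about 50% power for 0.35 against 0, so a non-significant difference must not be read as equal slopes. If a both-arms association was always intended, rewording Hypothesis 4 to say so would also remove the mismatch, but the trial would then not address the link under LDM that it now states.

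### Hypothesis 4 points to the wrong parent model: LV terms are added to the Aim 2 model, whose outcome is LV change, and the evident correction (Aim 1) brings in a site term without UAB

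*Combined protocol and SAP*

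**What the plan says.** Hypothesis 4 (sections II and VI) proposes that changes in LV systolic and diastolic function go along with changes in CFR. Its analysis paragraph (section VI, Aim 2, Statistical analyses) opens with the caveat that "temporality cannot be established in correlational analysis of concurrent changes". It then gives the model in two sentences.

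- The first lists treatment, baseline stratification variables, baseline CFR and baseline LV function as covariates, "as well as change in LV function, our outcome will be change in CFR".
- The second reads "By adding the baseline and change in LV function to our primary model for" Aim 2, and gives the purpose as exploring "whether changes in CFR are associated with changes in LV function, or whether independent treatment effects remain".

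The Aim 2 primary model is set out directly above, under Hypothesis 3: "We will use separate linear regression models with the respective change in LV peak GLS" and E' as outcomes. Its covariates include "imaging site (BWH, OHI, or UAB), the corresponding baseline LV peak GLS" or E' score. The Aim 1 model uses "separate linear regression models with the respective change in global CFR" and TPD at stress as outcomes, with "imaging site (BWH or OHI), the corresponding baseline global CFR score" among its covariates.

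Two other places bear on this. Section IV and the Aim 1 Methods give three PET imaging sites: BWH, OHI and UAB. Section V stratifies randomisation by time since the qualifying event, event type (MI or multivessel CAD), diabetes or metabolic syndrome, and site.

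**The concern.** The two modelling sentences of Hypothesis 4 are meant to describe one analysis, but they lead to models with different outcomes. The second, followed as written, is circular. If the reference is corrected to Aim 1, the analyst arrives at a model whose site term has no place for patients imaged at UAB. The paragraph also does not say whether GLS and E' enter separately or together, or which variables count as baseline stratification variables.

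At stake is a numbered hypothesis that carries the second half of Aim 2. Its specification should be fixed before the data are seen, so that the choice of LV measure and covariates cannot follow the results.

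**Working it through.** **1. The models side by side** (all from section VI)

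| Term | Hypothesis 4, first modelling sentence | Aim 2 model (Hypothesis 3) | Aim 1 model (Hypothesis 1) |
|---|---|---|---|
| Outcome | change in CFR | change in GLS, or in E' | change in global CFR |
| Treatment | yes | yes | yes |
| Baseline CFR | yes | no | yes |
| Baseline LV score | yes | yes | no |
| Change in LV | covariate | it is the outcome | no |
| Imaging site | levels not listed | BWH, OHI, UAB | BWH, OHI |
| Event type | only if section V strata are meant | no | no |

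Adding baseline and change in LV function to the Aim 1 column reproduces the first sentence, apart from the site and event-type rows. Adding them to the Aim 2 column does not: the baseline LV score is already there, the LV change is the outcome, and no CFR term appears.

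**2. What the literal model returns.** With T for treatment, X for the other covariates, LV0 for the baseline score and ΔLV for the change:

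ΔLV = a + b·T + c·X + d·LV0 + e·ΔLV + error.

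Least squares is solved exactly by e = 1 and a = b = c = d = 0, with zero residual. One simulated data set confirmed it (n = 130, 65 per arm; GLS difference 1.4 and SD 2.8 from Table 2, CFR difference 0.24 from Table 1, other inputs assumed):

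- Aim 2 model alone: treatment effect 1.47 (SE 0.52).
- Aim 2 model plus change in GLS: coefficient 1.000, R-squared 1.000, treatment effect 0 to machine precision.
- First-sentence model (outcome change in CFR): estimable, LV-change coefficient 0.031, R-squared 0.098.

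If the other LV measure were added instead, the model would not be circular, but it would still hold no CFR term.

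**3. The plan's own figure.** Hypothesis 4 has no power or sample-size figure. The nearest is 130 evaluable patients for 85% power on change in CFR (Table 1). Per arm, n = 2(1.960 + 1.036)² × 0.45² / 0.24² = 63.1, so 64, or 128 in total. This agrees with the stated 130 to within the normal approximation. The 130 is used below only as the number analysed.

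**4. Illustration: GLS and E' separately or together.** The correlations are assumed; the documents give none. Let r be the CFR–LV correlation given the covariates (the same for GLS and E'), and s the GLS–E' correlation. In a joint model the GLS term tests the partial correlation

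p = (r − r·s) / √[(1 − r²)(1 − s²)].

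Approximate power is Φ(atanh(p)·√(n − k − 3) − 1.96), where k is the number of other covariates: 7 in a separate model (treatment, diabetes stratum, time since MI, two site terms, baseline CFR, baseline LV) and 9 in a joint model. For r = 0.2:

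- Separate: 0.2027 × √120 − 1.96 = 0.26, power 60%.
- Joint, s = 0.3: p = 0.14/0.935 = 0.150; 0.151 × √118 − 1.96 = −0.32, power 37%.
- Joint, s = 0.5: p = 0.10/0.849 = 0.118; 0.118 × √118 − 1.96 = −0.67, power 25%.

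Simulation (10,000 trials per setting) gave the same powers. Significance of the GLS term differed between separate and joint models in 23% (s = 0.3) and 36% (s = 0.5) of trials. At r = 0.3, power was 92% separately and 72% or 52% jointly, with disagreement in 20% or 40%.

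**5. Illustration: two or three site levels.** Site shares follow from about 25 patients at each of six clinical sites, four of them imaged at BWH: 100, 25 and 25 of 150. UAB was merged with BWH in the two-level coding, which is an assumption, since the plan does not say where UAB patients would go. At r = 0.2, significance differed in 2.2% of trials, or in 11–12% if UAB is assumed to differ by 0.5 SD on both changes. At r = 0.3 the figures were 0.7% and 3.2%.

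**The case against.** The strongest reply is that only one workable model is on the page. The first sentence states the outcome and the covariates; the second, taken literally, cannot be a rival because it tests nothing. Replacing Aim 2 by Aim 1 restores agreement. This stands. A reader might infer that the analyst has to guess the outcome, but the documents do not support that: change in CFR is stated.

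A reader might also infer that the conclusion about "whether changes in CFR are associated with changes in LV function, or whether independent treatment effects remain" turns on whether CFR or LV function is made the outcome, and that the plan needs a mediation-type model. That comparison requires an LV-outcome model with CFR terms added, which appears in neither sentence. With change in CFR as the outcome, a remaining treatment effect is an effect on CFR. The plan promises an exploratory association with a proper temporality caveat, and not answering a mediation question is no defect.

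The LV measures can largely be inferred: GLS and E' are the Aim 2 primary endpoints, and Hypothesis 3 uses separate models. This too mostly stands, but Hypothesis 4 does not say so. Separate and joint coefficients are also different quantities, and the plan sets no significance rule for Hypothesis 4, so the percentages in steps 4 and 5 show sensitivity only.

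Last, the missing UAB level belongs first to the Aim 1 model. That is right, but it matters here because the natural correction leads straight to that model.

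**Conclusion.** The Hypothesis 4 analysis is wrong as written. Its second modelling sentence names a parent model that makes the analysis circular and contains no CFR term. This follows from the text and from algebra, and needs no assumption. That Aim 1 was meant is an inference, though a near-certain one. Correcting the reference alone would leave a site term that omits one of the three PET sites, and would leave open whether event type is among the promised stratification variables.

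Severity is minor. Hypothesis 4 is exploratory and correlational, and has no power claim. A reader might infer that the trial's primary result is in doubt; correcting Hypothesis 4 does not touch the randomised comparisons or the sample size. The figures for separate versus joint models (23–36% of trials at r = 0.2) and for site coding (2%, or 11–12% with a site shift) are illustrations that rest on assumed correlations and an assumed UAB difference. They are not estimates for this trial.

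**What to change.** Rewrite the Hypothesis 4 paragraph so that it states the following.

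1. The model is the Aim 1 change-in-CFR model with baseline and change in LV function added; replace the reference to Aim 2.
2. The site term has three levels: BWH, OHI and UAB. Bring the Aim 1 site term into line with the three PET sites.
3. GLS and E' are fitted in separate models, as in Hypothesis 3.
4. The coefficient of LV change is the test of Hypothesis 4. Any remaining treatment effect in this model is read as an effect on CFR only.
5. The covariates behind the term baseline stratification variables are listed and reconciled with section V, which includes event type: either include event type or state that it is left out and why.

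Keep the temporality caveat. The cost is a few sentences of wording and two regressions (GLS, E') on data already to be collected.
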